Hypothesis 1. We hypothesize that AUD/PTSD Veterans receiving PE+TOP will have fewer heavy drinking days at post-treatment and 3- and 6-month follow-up after active treatment compared with participants receiving PE+PLA.

Aim 2: To determine the relative efficacy of PE+TOP, as compared to PE+PLA, in reducing PTSD and depression symptoms in Veterans with comorbid AUD/PTSD at post-treatment and 3- and 6-month follow-up.

Hypothesis 2. We hypothesize that those receiving PE+TOP will show greater improvements in PTSD and depression symptoms at post-treatment and 3- and 6-month follow-up compared with participants receiving PE+PLA.

Aim 3: To determine the relative efficacy of PE+TOP, as compared to PE+PLA, in improving functioning and quality of life among Veterans with comorbid AUD/PTSD at post-treatment and 3- and 6-month follow-up.

Hypothesis 3. We hypothesize that AUD/PTSD Veterans receiving PE+TOP will show greater improvements in functional impairment and quality of life at post-treatment and 3- and 6-month follow-up compared with participants receiving PE+PLA.

Exploratory Aims: We will explore 1) the extent to which decreases in drinking and PTSD symptoms are associated with improvements in functioning; 2) whether PE completion and reductions in heavy drinking at post-treatment and follow-up in the PE+TOP condition are partially mediated by reduction in alcohol cravings and PTSD symptoms during the first half of treatment, and 3) whether reductions in cognitive functioning between baseline and mid-treatment will be associated with less PTSD symptom reduction and less reduction in subjective units of distress (SUDs) during imaginal exposure across PE sessions. Additionally, we will look for genetic associations with treatment response.

The proposed study is highly relevant to the goals of RR&D and the VA. It has the potential to improve functional and psychological recovery for a highly prevalent and highly impaired population of Veterans. This efficacy trial will test a novel and innovative combination of psychotherapy and medication with the goal of improving the care of Veterans. The successful completion of this project will help change the practices that drive treatment for Veterans with comorbid AUD and PTSD. The fundamental rationale for this study is to improve the evidence base that informs how patients with AUD and PTSD can attain sustained recovery from both of these disorders.

Section 7 - Background and Significance

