- **Power analysis:** We determined sample size for a two group design with PHDD as the primary outcome at post-treatment. A recent meta-analysis comparing the effects of TOP compared to placebo on heavy drinking found an overall standardized effect size of .406 [5]. The overall effect size was determined from seven studies with effect sizes ranging from .140 to .623. To ensure adequate power we calculated a sample size for a two-sample t-test by condition. The proposed primary analysis uses PHDD measured at baseline, post-intervention, 3, and 6 months in a random-intercepts regression model; however this use of additional data should serve to increase the power. A two-tailed test would require a sample size of 192 participants to detect an effect size of .406 with 80%. This is not a feasible sample size to recruit within the study's recruitment window. Alternatively, a 1-tailed test requires a sample size of 120 to have 72% power to detect the expected effect size. A one directional test is warranted given we are interested only in the improvement of PHDD for the TOP condition compared to the placebo condition. In addition, a sample size of N = 120 provides 80% power for a two-tailed test to detect a sample size of .516, a somewhat larger effect size within the range of effect sizes pooled in the recent meta-analysis [5]. Overall, we believe a sample size of N = 120 balances three needs: (1) sufficient power to compare the study groups; (2) the reality of recruiting a sample of Veterans with AUD and PTSD; and (3) overall project cost considerations.

Aims:

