- **Primary Aim Analysis.** As stated in Aim 1, we will evaluate the efficacy of PE+TOP, as compared to PE+PLA, in percent heavy drinking days (PHDD) among Veterans with comorbid AUD/PTSD at post-treatment and 3- and 6-month follow-up. The statistical model will be a generalized linear mixed model with a log link and gamma distribution variance function. If the over-dispersion parameter is close to zero a Poisson regression model will also provide equivalent model fit. The model will include a factor for treatment condition (PE+TOP, PE+PLA) and a linear term for time (baseline, post-treatment, 3, and 6 month follow-up). This model can be expanded to determine an adjusted intervention effect by including covariates such as gender and era of service. The primary test of treatment effect will be a group x time interaction. This flexible analytic method provides maximum likelihood parameter estimates based on all of the available data, allowing for the inclusion of cases with missing data and the modeling of the covariance error structure of the data across the

assessment points [90]. If the extent of missing data is small and the data appear to be consistent with a missing-at-random model, we will also carry out maximum-likelihood based on a “completer-analysis” using the observed data.

- **Secondary Aim Analyses.** As stated in Aims 2 and 3, veterans in PE+TOP, compared to PE+PLA, will show greater improvements in PTSD, depression symptoms, functional impairment and quality of life at post-treatment and 3- and 6-month follow-up. We will first examine the relationships among these outcomes to determine if composite scores should be created from highly correlated variables. This will help to reduce the number of statistical tests. The statistical model for these analyses will be random effects regression models as described in the primary aim analysis section, using identity link for Gaussian distributed linear variables and log or logit link functions for discrete or skewed outcome variables. These analyses would be in an intent-to-treat framework using maximum likelihood as before.

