- **Exploratory Aims:** First, we will explore the extent to which lower drinking and PTSD symptoms are associated with better functional outcomes. Analyses will build on the secondary analysis models, where functional impairment (WHODAS, WSAS) serve as the dependent outcome variables in GLMMs. The exploratory analysis measures of percent heavy drinking days (PHDD) and PTSD symptom severity (CAPS) will be added as time-varying covariates in separate GLMMs, to examine whether lower drinking and lower PTSD severity are associated with better functioning. We will also explore prospective or “lagged” effects for these time-varying covariates (PHDD /CAPS), to test temporal precedence as an indication of drinking/PTSD severity as potential mechanisms of improved functioning. Second, we will test the mediating effect of alcohol cravings and PTSD symptoms on the direct effect of the interventions on heavy drinking. Using the recommended analytic framework for multilevel mediation in interventions [91], separate HLMs will examine the “a” path (intervention effect on mediator) and “b” path (mediator effect on outcome). The mediated effect will be estimated using the product-of-coefficients approach and statistical significance estimated with 95% CI's via the bias-corrected bootstrap [92]. Third, we will test the mediating effect of change in cognitive functioning from baseline to mid-treatment on the strength of the direct effect of the intervention on PTSD symptoms and SUDs. The same analytic framework for testing statistical mediation will be used as described above.

Genetic Testing

- For each gene candidate we will conduct a 2 way repeated measures ANOVA on the data from the participants in the topiramate arm (approximately 74 participants), with genotype as a between subject factor and time (baseline, 2 mo, 5 mo and 8 mo) as a within subject factor. We predict that genotype will moderate change in CAPS scores over time as supported by a genotype X time interaction. The same analysis strategy will be used on the non-topiramate arm to determine if genotype affects overall treatment response, or only response specific to topiramate
- **Covariates:** ancestry, sex, medication status, and baseline CAPS scores. We will correct for multiple comparisons based on number of gene candidates tested as appropriate.

DNA Sampling

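### The sample size is set for the post-treatment PHDD difference, but the primary test is a group-by-linear-time slope whose power was never calculated and which isolates none of the visit differences in Hypothesis 1

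*Combined protocol and SAP*

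**What the plan says.** Section 6, Hypothesis 1, predicts that participants on PE+TOP "will have fewer heavy drinking days at post-treatment and 3- and 6-month follow-up after active treatment", compared with PE+PLA. That is a statement about the arm difference at three visits.

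Section 9, Power analysis, sizes the trial on one of them: "We determined sample size for a two group design with PHDD as the primary outcome at post-treatment". The test is a two-sample t-test and the effect size is 0.406. The result is that "a 1-tailed test requires a sample size of 120 to have 72% power to detect the expected effect size". The paragraph acknowledges that the analysis will differ: "The proposed primary analysis uses PHDD measured at baseline, post-intervention, 3, and 6 months in a random-intercepts regression model". It bridges the gap in one clause: "however this use of additional data should serve to increase the power".

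Section 9, Primary Aim Analysis, specifies a log-link gamma mixed model with "a factor for treatment condition (PE+TOP, PE+PLA) and a linear term for time (baseline, post-treatment, 3, and 6 month follow-up"), and then: "The primary test of treatment effect will be a group x time interaction". It names no visit-specific contrast. It gives neither the numerical coding of time nor the sidedness of the interaction test.

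**The concern.** The 72% belongs to one estimand (the post-treatment difference) and the primary p-value will come from another (the difference in linear slopes over four visits, baseline included). No calculation connects them.

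A slope rewards a gap that keeps widening through 6 months. Study drug stops after 16 weeks, so both follow-up visits are off drug. A benefit that appears by post-treatment and then holds steady is a step, which a straight line captures poorly; a benefit that appears and then shrinks may leave almost no slope. A real post-treatment effect of the planned size could therefore miss significance on the primary test.

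The claim that the extra visits add power depends on how the effect evolves after treatment and on the within-person correlation of PHDD. The documents give neither an arm difference at 3 or 6 months nor a correlation.

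**Working it through.** **Inputs from the documents.** Effect d = 0.406, N = 120, one-tailed (Section 9, Power analysis); 60 per arm (Section 10); random intercepts and four visits (Section 9). Drug is given for 16 weeks, with follow-up 3 and 6 months later (Section 9, Design), so the calendar months are about 0, 4, 7, 10.

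**Assumptions.** One-sided 5%; Gaussian approximation; complete data; equal SDs; correlation ρ = 0.3, 0.5 or 0.7.

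**The plan's own figure.** With 60 per arm, z = 0.406/√(2/60) = 2.224, so power = Φ(2.224 − 1.645) = 71.9%, or 71.4% by noncentral t. The stated 72% is correct for that t-test.

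**What the slope weighs.** With balanced data the weights are w = t − mean(t). Scaled so that baseline is −1, for baseline, post-treatment, 3 and 6 months:

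- visits 0, 1, 2, 3: (−1, −0.33, +0.33, +1)
- months 0, 4, 7, 10: (−1, −0.24, +0.33, +0.90)

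Post-treatment has a small negative weight. All the positive post-randomization weight sits on the two off-drug visits.

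**Power of the slope.** Let p be the effect at each visit as a fraction of d. Then z = d·Σwp / √((2/60)(1−ρ)Σw²). For a sustained effect, p = (0, 1, 1, 1), at ρ = 0.5:

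- visit coding: Σwp = 1.5, Σw² = 5, z = 0.609/0.2887 = 2.110, power 67.9%
- months 0/4/7/10: Σwp = 5.25, Σw² = 54.75, z = 2.1315/0.9552 = 2.231, power 72.1%

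**Alternatives with the same free baseline.** For a contrast c that sums to zero, z = d·c′p / √((2/60)(1−ρ)Σc²). For the three-visit average, c = (−1, 1/3, 1/3, 1/3) and Σc² = 4/3. At ρ = 0.5, z = 0.406/0.1491 = 2.724, power 86.0%.

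Power in %, for ρ = 0.3 / 0.5 / 0.7 (slope ranges span the two codings above):

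| Effect at post, 3 m, 6 m (× d) | Slope | Post-treatment change | Three-visit average |
|---|---|---|---|
| Sustained 1, 1, 1 | 56–60 / 68–72 / 86–89 | 59 / 72 / 89 | 74 / 86 / 97 |
| Half 1, 0.75, 0.5 | 18–22 / 22–27 / 31–38 | 59 / 72 / 89 | 53 / 65.5 / 84 |
| Gone 1, 0.5, 0 | 2–4 throughout | 59 / 72 / 89 | 31 / 39 / 54.5 |
| Delayed 0, 0.5, 1 | 65–67 / 77–79 / 93–94 | 5 | 31 / 39 / 54.5 |

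For a sustained effect the ranking of slope and average does not depend on ρ. The squared signal per unit variance is 1.5²/5 = 0.45 (visit coding) or 5.25²/54.75 = 0.503 (months) for the slope, against 1/(4/3) = 0.75 for the average. The slope is thus 60–67% as efficient.

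**Does the extra data raise power?** Under a sustained effect the slope beats the sizing t-test only when 1 − ρ is below 0.45 or 0.503, that is, when ρ exceeds 0.55 (visit coding) or about 0.50 (months).

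**Time coding.** The only list of these visits in months is in Section 9, Genetic Testing: "time (baseline, 2 mo, 5 mo and 8 mo) as a within subject factor". It does not fit 16 weeks of treatment. If it were used, the weights would be (−1, −0.47, +0.33, +1.13), sustained power 50/62/81% and the break-even correlation 0.62.

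**Baseline adjustment.** Adjusting for baseline gives the post-treatment contrast 75/82/93%, whatever happens later. At ρ = 0.5 the adjusted average has 96% (sustained), 83% (half) and 53% (gone). Part of that gain comes from the adjustment itself: a slope with a common baseline mean has 89–96%, 47–58% and 5–17% over the same three profiles and all three correlations.

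**Link function.** A marginal log-link gamma fit without a random intercept, at several assumed sets of PHDD means, kept the sign pattern: baseline −1, post-treatment −0.08 to −0.31, 3 months +0.19 to +0.34, 6 months +0.88 to +0.99. It does not give power for the planned model.

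**The case against.** The strongest reply is that under the protocol's own hypothesis little is lost. With a sustained effect and ρ = 0.5 the slope has 68–72%, close to the stated 72%, and at ρ = 0.7 it has 86–89%, so the sentence on added power would then be true. That is right: the sentence is unsupported rather than shown to be false. But the agreement at 0.5 is a coincidence of assumed values, and the three-visit average is better at every correlation in the same scenario.

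The very low powers come from fading patterns that the protocol does not predict. Section 7 reports that in a PE and naltrexone trial drinking rose in all groups by 6 months, least with the combination. That shows a common trend, not a shrinking arm difference. The fading cases are illustrations only.

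The slope is a valid test against a sustained effect, and it is clearly better than the average if benefit is absent at post-treatment and appears only later. If the effect grows (1, 1.25, 1.5), the slope (88–99.7%) about equals the free-baseline average (89/96/99.7%) and beats the post-treatment contrast. Late-only benefit is not what Hypothesis 1 says.

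The tabulated slope powers also assume no shared non-linear change. Both arms receive PE and medication counselling, so an early drop followed by a plateau is likely, and a linear model puts that curvature into its residual. Simulation with an assumed shared drop of 0.8, 0.7 and 0.6 SD at the three visits gave 51/61/77% for a sustained effect (visit coding) instead of 56/68/86%. On this point the table favours the slope. The 0/2/5/8 months belong to an exploratory analysis with time as a factor; they matter here only because the primary model states no coding.

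**Conclusion.** The concern holds. The 72% is correct for a post-treatment t-test but is not the power of the primary test, and the slope isolates none of the three differences that Hypothesis 1 names. The conclusion does not need the effect to fade: with a sustained effect, power at ρ = 0.5 is 68–72% for the slope against 86% for the three-visit average with the same free baseline. Fading makes it much worse (18–38% if halved by 6 months, 2–4% if gone, over ρ = 0.3 to 0.7).

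The mismatch is plain from the text. The sizes rest on a Gaussian random-intercept approximation, 60 complete cases per arm, one-sided 5% and assumed correlations; exact power under the log-link gamma model would differ. Because it concerns the test that decides the trial, this should be corrected.

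**What to change.** In the same mixed model, replace linear time with categorical visit (baseline, post-treatment, 3 months, 6 months), using a common baseline mean or baseline PHDD as a covariate. Pre-specify one primary contrast, with its sidedness and alpha:

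- **(a)** PE+TOP versus PE+PLA at post-treatment, which matches the sizing, followed by 3 and 6 months in fixed order; or
- **(b)** the average of the three post-baseline visits, which is closer to Hypothesis 1, with power restated for it.

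Delete the sentence on increased power, or state the persistence and correlation it assumes. If any linear time term stays, give its coding and reconcile the months in Genetic Testing with the 16-week treatment period in Design.

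The cost is plan wording and a few more model parameters; no new data are needed. Option (a) moves durability out of the primary test. Both options lose power relative to the slope if benefit appears only after treatment. The document is dated 10/04/2023 and does not show whether unblinded analysis has begun; the change must be made and dated before it does.

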Alcohol use disorder (AUD) and posttraumatic stress disorder (PTSD) frequently co-occur, and having one condition worsens the course of the other [15, 16]. Individuals with both disorders exhibit worse functioning across a number of domains than individuals with either disorder alone [e.g., 17, 18]. Prolonged exposure therapy [PE; 19] is among the most effective treatments for PTSD [3]. PE has been rated as a frontline treatment by multiple guidelines and reviews including the VA/DoD Clinical Practice Guidelines for the treatment of PTSD [20]. However, among samples with PTSD and AUD, changes in alcohol use following PE are only slightly better than in control or standard care conditions, reductions in PTSD symptoms are modest relative to studies of PE in PTSD patients without AUD, and rates of drop out from treatment are high [8]. Thus, studies of adjunctive treatments, such as medication, are critical to improve the benefits of PE for individuals who have AUD in addition to PTSD [4]; however, few studies have examined combining psychotherapy and medication [4] and none have examined Topiramate (TOP). TOP is the single medication that has shown effectiveness for both AUD and PTSD [3, 5] and shows promise for reducing drinking among individuals with AUD and PTSD [10]. The key next step is to test a best practice PTSD treatment, PE, together with a uniquely promising pharmacological agent, TOP.

The proposed study is designed to extend our prior research to identify effective treatments for comorbid AUD and PTSD with the goals of reducing problematic alcohol use and PTSD symptoms and improving functioning. We propose to use a randomized, controlled, double blind study design to examine the effect of adding TOP to a best practice treatment for PTSD, PE. Participants will be 120 male and female Veterans from all service eras with AUD and PTSD. Our central hypothesis is that PE+TOP will reduce alcohol use, ameliorate PTSD symptoms, and improve functioning and quality of life more than will PE+Placebo (PLA). Thus, there are three

specific aims and additional exploratory aims:

Aim 1: To determine the relative efficacy of PE+TOP, as compared to PE+PLA, in reducing heavy drinking among Veterans with comorbid AUD/PTSD at post-treatment and 3- and 6-month follow-up.

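### The exploratory genotype analysis of CAPS uses a repeated-measures ANOVA with no rule for missed visits; a maximum-likelihood mixed model would keep participants with incomplete data

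*Combined protocol and SAP*

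**What the plan says.** In Section 9, Genetic Testing, the plan states: "For each gene candidate we will conduct a 2 way repeated measures ANOVA on the data from the participants in the topiramate arm". Genotype is the between-subject factor, and time has four levels (baseline and three later visits). The test of interest is the interaction: "We predict that genotype will moderate change in CAPS scores over time as supported by a genotype X time interaction". The analysis is repeated in the non-topiramate arm. The listed covariates are ancestry, sex, medication status and baseline CAPS. Nothing is said about a participant who misses a visit. The Missing Data paragraph opens with the primary outcome and does not mention the genetic analysis.

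PTSD symptoms are handled differently under Secondary Aim Analyses: "The statistical model for these analyses will be random effects regression models as described in the primary aim analysis section", and "These analyses would be in an intent-to-treat framework using maximum likelihood as before". The Primary Aim Analysis to which this refers describes maximum likelihood on all available data, "allowing for the inclusion of cases with missing data". The Exploratory Aims paragraph names the CAPS as its measure of PTSD symptom severity.

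On attrition, Section 6 says of earlier prolonged-exposure studies in PTSD with alcohol use disorder that "rates of drop out from treatment are high".

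**The concern.** A classical repeated-measures ANOVA with four time levels needs all four scores from each person. One missed visit removes the person and the scores that were collected. Within a single arm, split again by genotype, there are few people to spare. The plan already accepts, for PTSD symptoms, a method that keeps such people, and it gives no reason for departing from it here.

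At stake are the power of the genotype x time test and its consistency with the treatment analyses. The two would describe different sets of participants.

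**Working it through.** **The plan's own figures.** The genetic Power Analysis gives 0.9 power for N = 75 and f = 0.4, with 2 genotype levels and 4 times. It states neither alpha nor the correlation between visits, so 0.9 cannot be confirmed. At an assumed 5% level:
- The between-genotype test gives 0.991 at correlation 0.5 and 0.945 at 0.9.
- The interaction test gives about 1.00 with λ = f²·N·m/(1−ρ), where m = 4, or 0.83 with λ = f²·N.

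The companion t-test figure (d = 0.75, power 0.8) does reproduce: 0.796 with a 19 v 56 split of 75. None of these figures allows for incomplete visits.

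**Inputs from the documents.** There are four CAPS time points. Section 10 gives 60 per arm, and Genetic Testing gives about 74 for the topiramate arm. The two disagree, so both are used. The genetic Power Analysis gives a 25/50/25 genotype split, taken here as 25 v 75 for two levels.

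**Assumptions.** Correlation 0.6 between visits, a 0.6 SD genotype effect at each of three follow-ups, 5% level, and missingness completely at random.

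**Complete-case power by formula.** For the 3-df genotype x visit test, λ = (n₁n₂/n) × Σ(δⱼ − δ̄)² / (1 − ρ).
- δ = (0, 0.6, 0.6, 0.6) and δ̄ = 0.45, so the sum is 0.45² + 3 × 0.15² = 0.27, and 0.27/0.4 = 0.675.
- With a 25 v 75 split, n₁n₂/n = 0.1875n, so λ = 0.1266n.
- Power is the chance that a noncentral chi-square on 3 df exceeds 7.815.

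**Number with all four visits.** Under independent missingness m per follow-up visit this is N(1 − m)³. Under monotone dropout totalling d it is N(1 − d).

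**Results for N = 60.** The simulations used 1,500 runs and known covariance. Monte Carlo error is at most √(0.25/1500), about 1.3 points.

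| Missingness | With all four visits | λ | Complete case, formula | Complete case, simulated | All data, simulated |
|---|---|---|---|---|---|
| None | 60 | 7.59 | 63% | 64% | 64% |
| Independent, 10% per visit | 43.7 | 5.54 | 48% | 47% | 61% |
| Independent, 15% | 36.8 | 4.66 | 41% | 42% | 60% |
| Independent, 20% | 30.7 | 3.89 | 35% | 34% | 60% |
| Monotone, 10% in total | 54 | 6.83 | 58% | 59% | 63% |
| Monotone, 20% | 48 | 6.08 | 52% | 53% | 59% |
| Monotone, 30% | 42 | 5.32 | 47% | 46% | 56% |
| Monotone, 40% | 36 | 4.56 | 40% | 40% | 55% |

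The gap is 14 to 26 points for scattered missed visits and 4 to 15 points for monotone dropout. At N = 74 the gaps are similar, about 3 to 26 points.

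**Second set of assumptions** (correlation 0.5, 0.75 SD effect, 10, 15 and 20% missing per visit).
- N = 60: 58 v 68, 48 v 65 and 41 v 61%.
- N = 74: 65 v 75, 58 v 73 and 50 v 73%.
- With no missing data the two methods agree (74% at N = 60, 81% at N = 74).

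**The case against.** The strongest reply is that dropout from treatment is not the same as a missing assessment. The Data Management paragraph says staff will try to obtain post-randomization data even from people who leave treatment. Section 9 allows visits by phone, mail or telehealth. Section 15 schedules a final evaluation within a week for discontinued participants. The high dropout in Section 6 describes earlier studies. This stands: the documents give no rate of assessment loss, and the loss could be small. It limits the problem but does not remove it, because the text promises an attempt and the ANOVA drops a person for a single missed visit.

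The size of the gap also depends on the pattern. Independently missed visits favour the mixed model most, and under monotone dropout the advantage shrinks. This stands too, which is why both patterns are shown.

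Two steps are inference. The plan does not say that incomplete participants are excluded; that follows from the standard form of the named method, with no alternative given. The secondary-aims text says PTSD without naming an instrument and allows composite scores; the link to CAPS comes from the Exploratory Aims paragraph. Both inferences are reasonable.

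A reader might also infer that completers respond better and that the genotype result is therefore biased. The documents do not say so, and the simulations above delete visits at random, so they cannot show it. In a separate check that made dropout depend on the previous CAPS score, the complete-case change from baseline was biased (−0.73 to −0.75 SD against a true −0.80), but the genotype contrast was not materially affected.

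**Conclusion.** The point holds as a minor one. The named method, in its standard form, discards participants with any missed visit, while the plan's analysis of PTSD symptoms keeps them. With complete data the two approaches agree, so nothing is lost by changing.

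The power cost at N = 60 ranges from about 4 points (monotone dropout totalling 10%) to about 26 points (20% of each follow-up visit missed independently). These figures rest on the assumed effect, correlation, genotype split and missingness. The planned correction for the number of genes would lower power for both methods.

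The documents do not support two stronger readings: that a large part of the arm will certainly be lost, or that the genotype estimate is biased in a known direction. Bias is possible if missingness depends on earlier scores, but it is not shown. The analysis is exploratory, and no primary or secondary conclusion depends on it.

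**What to change.** In Genetic Testing, replace the repeated-measures ANOVA with a maximum-likelihood mixed model for CAPS on all available visits, fitted in each arm as now planned. Include genotype, visit as a categorical factor and genotype x visit, with a joint test of the interaction terms, plus ancestry, sex and medication status.

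Two details need stating. First, a plain cross-reference to the secondary-aims model is not enough, because that model takes over a linear time term from the primary analysis and has no genotype term. Second, baseline CAPS is now both a level of the outcome and a covariate. Keep it as one or the other: with four outcome levels, drop the covariate; with baseline as covariate, model the three later visits only.

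The cost is a change to the analysis text and the specification of one model. It needs no new data, visits or participants.
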